### 8) Data and Specimen Management and Confidentiality

### Recruitment:

Subjects will be recruited through the FXS clinics at the University of Alberta and CHU Sainte-Justine as well as by referral from other centers in Canada. The University of Alberta site will also recruit patients from other centers across Canada (including in Alberta, Manitoba, Saskatchewan, and British Columbia) referred to the study. The Universite de Montreal site will also recruit patients from the Maritimes, Quebec, and Ontario referred to their center. This way, any FXS patient from Canada will be able to participate in the study if they want. Approved study information material will be posted on intellectual disability, autism, and FXS support group websites and social media feeds, and in clinical spaces.

Educational and scientific conferences by the Co-I to health professionals, education systems, and other individuals interacting with FXS patients and families will also be used to disseminate knowledge about the study and recruitment. A website for the study has been created with videos and testimonial from clinicians, researchers, patients, and family members to generate interest and facilitate recruitment.

Potential subjects/caregivers who are interested in participating in the study will be able to contact a study team member to schedule their visit 1. This will also allow potential subjects/caregivers to ask study-related questions and discuss the study in depth with the research team. The research team will use a pre-screen form where questions will be asked to the participant/caregiver over the phone to determine if the participant will be eligible to continue to visit 1. Informed consent will be signed at the first visit. Informed consent includes authorization to access and use their health information for the research study. For participants followed at CHU Ste-Justine, the study team is authorized to access medical records of CHU Ste-Justine patients to verify eligibility prior to getting their consent for the trial.

### Confidentiality:

Participant confidentiality and privacy are strictly held in trust by the participating investigators, their staff, and the sponsor(s) and their interventions. This confidentiality is extended to cover to the clinical information relating to participants. Therefore, the study protocol, documentation, data, and all other information generated will be held in strict confidence. No information concerning the study or the data will be released to any unauthorized third party without the prior written approval of the sponsor. Study files will be kept in a locked cabinet in a locked room with access restricted to research staff.

All research activities will be conducted in the Stollery Children's Hospital and the Biological Sciences building at the University of Alberta in as private a setting as possible.

The study monitor board, other authorized representatives of the study sponsor (Women and Children's Health Research Institute, Fondation CHU Ste-Justine), representatives of the

Research Ethics Board (REB) or regulatory agencies may inspect all documents and records required to be maintained by the investigator, including but not limited to, medical records (office, clinic, or hospital) and pharmacy records for the participants in this study. The clinical study site will permit access to such records.

The study participant's contact information will be securely stored at each clinical site for internal use during the study. At the end of the study, all records will continue to be kept in a secure location for the period dictated by Health Canada regulation (25 years).

De-identified study participant research data, which is for purposes of statistical analysis and scientific reporting, will be stored in the REDCap electronic data capture system at the Women and Children's Health Research Institute (WCHRI) Data Coordinating Centre (DCC) at the University of Alberta. This data will not include the participant's contact or identifying information. Rather, individual participants and their research data will be identified by a unique study identification number. Permission to store data at the WCHRI DCC will be included in the informed consent.

WCHRI's REDCap installation is housed in a secure data centre at the University of Alberta Hospital and is behind the Faculty of Medicine & Dentistry's firewall. Data is entered through a web based interface using 128 bit SSL encryption. Login is via a username/password pair with additional two factor authentication (2FA). Additional information is available in WCHRI's privacy document (https://redcap.ualberta.ca/privacy.pdf).

Coordinators and investigators at each study site will only have access to data relating to their own study participants. Study management staff (PI and research coordinator) at the lead site will have access to data for all study participants. Staff at the WCHRI DCC will have access to data for all study participants. This access is required to perform system management functions, data cleaning, and analysis. Once the study database is "locked" and data has been extracted for analysis, read only access to the study database will be granted to the PI and/or their designate if requested.

We will have a material transfer agreement between the Canadian sites and a research institute in the United States (UC Davis MIND Institute) that plans to collect similar data, with the hopes that it may contribute to the research endpoints. This collaboration may include additional biomarker studies. With a material transfer agreement, each site may have access to blood epithelial cells cultured from urine and fibroblasts of patients at other sites for future research, if the patient consents to this use, in which case all such specimens would be de-identified upon transfer.

Analysis will be based on the intention-to-treat principle. The team at the University of Alberta, Ste-Justine, and MIND Institute will collaborate on data analysis. The data will be merged into one dataset shared and analyzed across the different sites. De-identified data will be shared across sites as stated in the consent form including the UC Davis and Ste-Justine forms. Data will

also be analyzed in the lab of [name] using machine learning approaches and advanced statistical analysis, as well as proteomics on urine samples.

The analysis of treatment efficacy will be based on the analysis of covariance (ANCOVA) with outcomes (receptive and expression language at 4-month follow-up with corresponding baseline measure as a covariate). The chosen endpoint at 4-month, based on preliminary data, provides a reasonable treatment time period to assess changes in the response. The proposed method adjusts for potential baseline differences between treatment arms despite randomization, if any. The sample size/power for the ANCOVA is based on sample size needed for a t-test by a variance inflation factor 1-2 where there is the correlation between baseline and follow-up measures. From our preliminary data, the receptive and expressive scores have ranges from approximately 0.2 to 0.5. Thus, we predict power for the t-test and power for the ANCOVA will be higher depending on this factor. We estimate clinically relevant effects sizes, based on our preliminary data, at follow-up visit as follows (metformin/placebo): receptive language score mean 18.1/23.8, SD=7.0; expressive language score mean 13.6/20.7, SD=8.4. For these effect sizes of the 2 primary measures, the ANCOVA will have power of at least 80% (or have between 0.2-0.5) at level alpha=0.016 with the proposed total sample size n = 60 for each group (placebo and treatment).

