In addition, metformin inhibits phosphodiesterase, which would lead to correction of cAMP levels. Moreover, metformin inhibits MMP9 production, which is also elevated in FXS (Hoeffer et al., 2012; Muzar et al., 2016; Dziembowska et al., 2013), and MMP9 as a biomarker will be assessed in this proposal. Looking at the potential signaling pathways, metformin appears to be a good candidate for targeting several of the intracellular functions in neurons disrupted in FXS and therefore possibly rescuing several types of symptoms in individuals with FXS.

[name] team (MIND Institute) has utilized metformin in the clinical treatment of over 20 individuals with FXS between the ages of 4 and 58 years and have found benefits not only in lowering weight gain and normalizing appetite, but also in language and behavior with doses up to 1000 mg twice a day (Dy et al., 2017). [name] team has recently reported in Dy et al. (2017) the details of the first 7 patients treated clinically for whom pre and post Aberrant Behavior Checklist results were obtained and documented improvement in weight, language, and behavior. This medication has been well tolerated, even in the 4-year-old patient with FXS, and it is time now to carry out a controlled trial.

Considering these promising preliminary results and the established safety of metformin in children, we propose to carry out a randomized, placebo-controlled trial of metformin to further assess safety and benefits in the areas of language/cognition, eating, and overall behavior, in addition to weight loss. The trial will include a US site at the MIND Institute and two Canadian centers (University of Alberta and CHU Sainte-Justine).

This study also provides an opportunity to carry out novel outcome measures that are capable of documenting improvements in the processing of information in the CNS (event related potentials (ERPs) and Tobii eye tracking), cognitive abilities (NIH Toolbox cognitive battery measures and expressive language sampling), critical biomarkers of involvement by the *FMR1* 

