#### Treatment Measures:

Expressive Language Sampling (ELS) - Expressive language samples will be collected from each participant twice, at study baseline and at the end of treatment/week 16. At each assessment, samples will be collected in two different contexts: conversation and narration. In conversation, the examiner engages the participant in talk on a variety of topics (e.g., school) according to guidelines that specify the order of topics and the ways in which topics are introduced and maintained. In narration, the participant tells the story in a wordless picture book. The examiner prompts and responses are scripted. In both contexts, the examiner follows a script that minimizes his/her participation, maximizes the participant's contribution, and avoids the use of examiner language that would constrain the participant's talk. In both conversation and narration, all talk is digitally recorded and transcribed by highly experienced transcriptionists following procedures that yield high intertranscriber agreement (Abbeduto et al., 1995). Computerized analyses of the transcripts characterize multiple dimensions of the talk produced by the participant (e.g., vocabulary diversity, syntactic complexity). The mean Number of Different Words (NDW) in conversation and in narration will be computed (and statistically adjusted through analysis of covariance for differences in talkativeness as suggested by Conners et al., 2018) and serve as the primary outcome measure. This measure has been shown to have excellent test-retest reliability, display negligible practice effects, be free of floor and ceiling effects, have good construct validity for individuals with FXS, and improve with treatment (Berry-Kravis et al., 2013; Channell et al., 2018; McDuffie et al., 2016). For French speaking participants, we will use a French translation of the ELS.

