### 14) Multi-Site Research

This trial has a multi-site design. The study sponsor/PI has obtained a material transfer agreement with an additional international research institution (UC Davis MIND Institute) that will collect similar data to contribute to the research endpoints. With the material transfer agreement, de-identified data as well as de-identified biological samples including blood, urine endothelial cells, and fibroblast lines would be shared to compare biomarkers that are outlined in this study (see Section 7). All results and data will be de-identified to protect the confidentiality of

the research subjects. Allocation tables generated by the Data Coordinating Centre statistician have been uploaded to REDCap and sent to the Alberta Health Services Pharmacy Research Office (University of Alberta) and SPSR (CHU Sainte-Justine, University of Montreal). Once the study coordinator has randomized a participant in REDCap (done separately for each site), the randomization number that is generated will be sent to the respective pharmacy, which will then prepare the drug or placebo based on the number they are given and the table that has been provided to them by the DCC.

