### Randomization:

Allocation tables generated by the Data Coordinating Centre statistician have been uploaded to REDCap and sent to the Alberta Health Services Pharmacy Research Office (University of Alberta) and SPSR (CHU Sainte-Justine, University of Montreal). Once the study coordinator has randomized a participant in REDCap (done separately for each site), the randomization number that is generated will be sent to the respective pharmacy, which will then prepare the drug or placebo based on the number they are given and the table that has been provided to them by the DCC.

Participants will be randomized to treatment or control arm with a 1:1 allocation ratio, stratified by sex and using permuted blocks of randomly varied sizes 2 and 4. Participant randomization will be performed in REDCap, based on allocation tables that have been generated and uploaded by the Data Coordinating Centre statistician. REDCap maintains an automated audit trail which includes the assigned study identification number, treatment allocation, and date and time of the transaction.

The randomization process will be performed the same way at both sites, i.e. randomization to treatment or control arm with a 1:1 allocation ratio stratified by sex and using permuted blocks of randomly varied sizes 2 and 4.

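### The stated efficacy ANCOVA adjusts only for baseline, although allocation is stratified by sex and run by site: the test may be slightly conservative (minor, near-free improvement)

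*Combined protocol and SAP*

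**What the plan says.** The efficacy model stands in Section 8, in the analysis paragraph at the end of the Confidentiality text. It is an ANCOVA with outcomes "receptive and expression language at 4-month follow-up with corresponding baseline measure as a covariate". The same paragraph claims at least 80% power at alpha 0.016.

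Section 18 (Randomization) sets 1:1 allocation, "stratified by sex and using permuted blocks of randomly varied sizes 2 and 4". It adds "Once the study coordinator has randomized a participant in REDCap (done separately for each site" and "The randomization process will be performed the same way at both sites". Sex is therefore the declared stratification factor, and site is one in effect.

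Section 8 also says "The data will be merged into one dataset shared and analyzed across the different sites". Section 3 says "The trial will include a US site at the MIND Institute and two Canadian centers", and Section 14 describes "an additional international research institution (UC Davis MIND Institute) that will collect similar data to contribute to the research endpoints". The randomisation text covers only the two Canadian sites.

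The one other adjustment named is in Section 7 (Expressive Language Sampling), where the number of different words is adjusted by ANCOVA for talkativeness. Neither sex nor site is named there.

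**The concern.** Blocking within sex and site forces the arms to be nearly balanced on both. If either factor predicts outcome beyond baseline, the treatment estimate already varies less from trial to trial because of that balance. A model without the factors leaves their variance in the residual and does not credit the balance. Its standard error is then too large, its intervals too wide, and its test conservative.

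What is at stake is some efficiency, and an analysis that matches the randomisation.

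**Working it through.** **Inputs from Section 8.** Receptive score: difference 23.8 − 18.1 = 5.7, SD 7.0, so 5.7/7.0 = 0.814 SD. Expressive score: 20.7 − 13.6 = 7.1, SD 8.4, so 0.845 SD. Alpha is 0.016, taken as two-sided because the side is not stated. The range 0.2 to 0.5 is read as the baseline to follow-up correlation ρ; its symbol is missing from the text. The sample is 60 per arm. Section 5 supports this with 60 participants at each site: 2 × 60 = 120. The sentence in Section 8 mixes a total with a per-group figure, so 30 per arm is shown as a sensitivity case.

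**The plan's own figure.** SE = SD × √(1 − ρ²) × √(2/n). Receptive, ρ = 0.2, n = 60: 7.0 × 0.980 × 0.1826 = 1.252. Then 5.7/1.252 = 4.55, and 4.55 − 2.41 = 2.14, which is 98.4% power (99.7% at ρ = 0.5). The claim of at least 80% is met without sex or site in the model. At 30 per arm the same formula gives 79.1% and 89.1%.

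**What leaving out the factors does.** Let sex and site together explain a share τ of outcome variance. This is an assumption; the documents give no value. The gaps are taken as equal at both visits, the whole-sample SD is 1, and strata balance is exact. The correlation within strata is ρw = (ρ − τ)/(1 − τ). The variances are:

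- reported by the baseline-only model: 1 − ρ²
- actual, for that model's estimate: (1 − τ) − 2ρ(ρ − τ) + ρ²(1 − τ)
- with sex and site added: (1 − τ)(1 − ρw²)

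Each SE is √(2 × variance/60). At τ = 0.20:

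| ρ | Reported SE | Actual SE | SE with sex + site | Reported/actual |
|---|---|---|---|---|
| 0.2 | √(0.960/30) = 0.1789 | √(0.832/30) = 0.1665 | √(0.800/30) = 0.1633 | 1.07 |
| 0.5 | √(0.750/30) = 0.1581 | √(0.700/30) = 0.1528 | √(0.6875/30) = 0.1514 | 1.04 |
| 0.8 (assumed) | √(0.360/30) = 0.1095 | √(0.352/30) = 0.1083 | √(0.350/30) = 0.1080 | 1.01 |

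At τ = 0 the three SEs are equal. As ρ rises, baseline absorbs the sex and site gaps and little is left to gain.

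**Power.** This was simulated with blocks of 2 and 4 within site by sex, two equal sites and 25% female (both assumed), and 8,000 trials per cell. Entries are % power, baseline only → with sex and site. Near 64%, the Monte Carlo error of one entry is about √(0.64 × 0.36/8,000) = 0.5 points.

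| n per arm, effect | ρ | τ = 0 | τ = 5% | τ = 10% | τ = 20% |
|---|---|---|---|---|---|
| 60, 0.814 SD (plan) | 0.2 | 98.1→98.1 | 98.4→98.5 | 98.4→98.7 | 98.6→99.4 |
| 60, 0.814 SD (plan) | 0.5 | 99.6→99.5 | 99.7→99.7 | 99.8→99.8 | 99.7→99.8 |
| 60, 0.5 SD (assumed) | 0.2 | 63.5→63.6 | 64.1→65.5 | 63.3→66.8 | 63.8→72.1 |
| 60, 0.5 SD (assumed) | 0.5 | 75.9→76.0 | 76.4→77.0 | 76.3→77.7 | 76.0→79.5 |

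At 30 per arm and 0.814 SD, the range over τ = 0 to 20% runs from 75.6→75.2 to 76.6→83.2 at ρ = 0.2. At ρ = 0.5 it runs from 86.6→86.6 to 87.8→89.9. At an assumed ρ of 0.8 with 60 per arm and 0.5 SD, power moves 98.0→98.0 at τ = 10% and 98.2→98.4 at 20%.

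**Hand check of the largest 60-per-arm gain** (ρ = 0.2, τ = 20%, 0.5 SD). Baseline only: (0.5 − 2.444 × 0.1789)/0.1665 = 0.377, or 64.7%. With sex and site: 0.5/0.1633 − 2.445 = 0.617, or 73.1%. This agrees with the simulated 63.8→72.1 within about 1 point. Here ρw = (0.2 − 0.2)/0.8 = 0, meaning no baseline to follow-up correlation within strata, so this is a corner case.

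**Type I error** (simulated, 60 per arm, τ = 20%). The baseline-only model gives 1.0% at ρ = 0.2 and 1.4% at ρ = 0.5, against the nominal 1.6%. With sex and site it is 1.6% in both.

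**The case against.** The strongest reply is that no harm is shown. A baseline-only ANCOVA is valid here and errs, if at all, on the conservative side. Section 8 is a short outline leading into the power calculation, and it does not say that baseline is the only covariate. Both points stand. They make this a request to state the model fully.

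The inputs can also be challenged. The correlations and effects in Section 8 belong to receptive and expressive scores, whereas Section 7 makes the number of different words the primary measure and reports excellent test-retest reliability for it. If its correlation is well above 0.5, the gain nearly vanishes, as the ρ = 0.8 figures show. This also stands. It limits the size of the gain and leaves its direction unchanged.

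Three stronger readings are tempting, and the documents do not support them.

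- A reader might infer a biased estimate or inflated false-positive risk. The stated 1:1 allocation within sex at each Canadian site rules out the first, and the type I figures contradict the second.
- A reader might infer that the power claim fails. At 60 per arm it is met with a wide margin.
- A reader might count test language as an omitted stratification factor, since "For French speaking participants, we will use a French translation of the ELS". Language is not used in allocation, so leaving it out does not by itself make the test conservative. It is not part of this point.

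The US site's allocation scheme is not described, so the balance argument is shown only for the two Canadian sites.

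**Conclusion.** The point holds as a minor matter of efficiency. The only stated efficacy model leaves out sex and site, the two factors by which the Canadian sites randomise. If they predict outcome beyond baseline, the reported standard error is too large: by up to about 7% at ρ = 0.2 and 4% at ρ = 0.5, for an assumed 20% variance share. If they do not, nothing is lost.

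The gain in power is unknown and may be zero. It is about 0 to 1 point at the plan's own effect with 60 per arm, and near zero at a high correlation. At 60 per arm it reaches as much as about 8 points only with an assumed 0.5 SD effect, a correlation of 0.2 and a 20% share. At 30 per arm the most is about 7 points. All variance shares, the sex ratio and equal site sizes are assumptions.

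**What to change.** State the primary model in the analysis paragraph as week-16 outcome = treatment + baseline + sex + site. Keep the talkativeness adjustment of Section 7 and say whether it enters this model as a covariate. If US data are merged into the analysis, give that site its own level.

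The change is one sentence, needs no new data, and should be settled before unblinding. It uses 2 degrees of freedom, or 3 with a US level. If sex and site explain nothing, power at 60 per arm is unchanged to within 0.1 point (63.5→63.6 and 75.9→76.0 at 0.5 SD). At 30 per arm the loss is about 0.4 points at most (75.6→75.2 at 0.814 SD).

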## Data Safety and Monitoring Board (DSMB):

A DSMB for the Canadian centers located at the University of Alberta will collaborate and exchange information with the DSMB of the US site at the MIND Institute. The Canadian DSMB will include a minimum of two physicians who are independent of this study but who have significant expertise in carrying out psychopharmacological interventions in individuals with FXS. In addition, an independent statistician not involved with the study will be a member of each DSMB. The DSMBs will examine unblinded adverse events and clinical data on a semi-annual basis to review study progress and to advise whether the trial can be safely continued. The investigators and study staff will remain blinded throughout the trial. Any serious adverse events (SAEs) will be reported to the REB of each site and Health Canada in accordance with their respective reporting guidelines.

# 9) Data and/or Specimen Banking

### Retention of Records:

Data will remain in REDCap system at the WCHRI DCC until all data management and statistical analysis activity has been completed. Following study completion and publication, the data will be deleted from the REDCap system.

The WCHRI DCC will facilitate the deposit of de-identified data in a publicly accessible, secure and curated repository for discovery and reuse by others in accordance with the Tri Agency Statement of Principles on Digital Data Management (2017). This will include creating a public

metadata in an open source system, such as Dataverse or Dryad. This could then be used by other investigators as a starting point to contact you if they want to collaborate and/or access deidentified data sets.

The PI will be responsible for storing copies of the data and other study materials in a secure archival facility in compliance with Health Canada and local institutional research data retention policy. At the end of this retention period these materials will be destroyed.

